Specific Aims and Hypotheses

Aim 1. To study the effectiveness of antidepressant medications to treat depressive symptoms in older adults with PTSD/MDD.

Hyp 1: A significant improvement in depressive symptoms will be observed, and response rates to open antidepressant medication treatment in this population will be greater than 50%.

Aim 2: To evaluate change in cognition and physical function following antidepressant medication treatment.

Hyp 2: As compared to non-responders, responders to antidepressant treatment will demonstrate significantly greater improvement in executive function (NIH Toolbox) and gait speed.

Description of Subject Population

Sample #1

Specify subject population

Participants in IRB 7489 with combined PTSD and MDD

Number of completers required to accomplish study aims

20

Projected number of subjects who will be enrolled to obtain required number of completers

25

Age range of subject population

50 years and older

Gender, Racial and Ethnic Breakdown

We anticipate the sample will be composed of approximately 60% women and 40% men.

Racial/ethnic group: On the basis of previous depression studies conducted in the Clinic for Aging, Anxiety, and Mood Disorders, it is anticipated that the sample will be composed of approximately 75% Caucasian, 15% African American, and 10% Hispanic subjects.

Description of subject population

The proposed study will enroll 25 outpatients who are (1) participants in IRB 7489, (2) diagnosed with DSM 5 MDD, (3) have HRSD ≥ 18 , and (4) are willing to and capable of providing informed consent and complying with study procedures. Participants will be excluded for (1) history of allergic or adverse reaction to escitalopram and duloxetine, (2) non-response to adequate trial of escitalopram (at least 4 weeks at dose of 20mg) and duloxetine (at least 4 weeks at dose of 60mg) during the current episode, or (3) current treatment with psychotherapy, antidepressants, or other psychotropic medications.

Recruitment Procedures

Describe settings where recruitment will occur

Subjects will be recruited from participation in IRB 7489.

How and by whom will subjects be approached and/or recruited?

The research assistant will notify a study clinician once a participant completing IRB 7489 is known to meet the selection criteria. The clinician will then approach the participant and discuss potential treatment in this protocol, with its attendant risks, benefits, and alternatives.

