3. HRSD >=18

3. Data from IRB 7489

4. Willing to and capable of providing informed consent and complying with study procedures.

4. Clinical interview

Create or insert table to describe the exclusion criteria and methods to ascertain them

Exclusion criteria:

Method of ascertainment:

1. History of allergic or adverse reaction to escitalopram and duloxetine

1. Clinical interview, data from IRB 7489

2. Non-response to adequate trial of escitalopram (at least 4 weeks at dose of 20mg) and duloxetine (at least 4 weeks at dose of 60mg) during the current episode

2. Clinical interview, data from IRB 7489

3. Current treatment with psychotherapy, antidepressants, or other psychotropic medications.

3. Clinical interview, data from IRB 7489

Waiver of Consent/Authorization

Indicate if you are requesting any of the following consent waivers

Waiver of consent for use of records that include protected health information (a HIPAA waiver of Authorization)

No

Waiver or alteration of consent

No

Waiver of documentation of consent

Yes

Waiver of parental consent

No

Consent Procedures

Is eligibility screening for this study conducted under a different IRB protocol?

Yes

Indicate NYSPI IRB #

7489

Describe Study Consent Procedures

Participants who complete IRB 7489, meet the study selection criteria and agreed to be contacted in the future will be approached by a study clinician, Psychiatrist (MD), or a Psychiatric Nurse Practitioner (NP) authorized to obtain patient consent. Study clinicians who obtain consent for this study are licensed Doctors of Medicine (MD) and/or Psychiatric Nurse practitioners (NP) in the State of New York. Participants may be approached on the day of their final study visit for protocol IRB 7489 or may be contacted by phone.

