1. Following consent, the participant will be begun on either escitalopram 10mg or duloxetine 30mg. The default medication will be escitalopram. Subjects will begin escitalopram 10mg, continue this dosage for 4 weeks, then if the HRSD >7 at Week 4, he/she will have their dosage increased to 20mg for the remainder of the 8 week study. Participants who have not responded to or not tolerated escitalopram in the current depressive episode will be started on duloxetine. They will take 30mg of duloxetine for the first 2 weeks, then, **contingent on clinical assessment that the 30mg dose is sufficiently well tolerated**, be increased to 60mg for the **remaining 6 weeks** of the study. Participants will be provided with the study medication during the Week 0 (baseline) in person visit. During the week 4 (virtual) visit, participants **taking escitalopram** will be sent the study medication directly to their home via Fedex. **This will be done during the week 2 (virtual) visit for participants taking duloxetine.** If significant worsening occurs and/or the participant wishes to be seen in person for the week 4 **or week 2** visit, they will be provided with the study medication onsite.

Study Visits will occur in person/virtually as outlined below:

- Week 0: In-person
- Week 2: Virtual
- Week 4: Virtual
- Week 6: Virtual
- Week 8: In-person

2. Subjects unable to tolerate the higher dose of study medication will have their dose reduced to the previously tolerated dose. Subjects unable to tolerate the beginning dose of study medication will be tried (if possible given their history) on the other study medication. Participants unable to tolerate the beginning dose of either study medication will be dropped from the study and enter post protocol open treatment.

3. Subjects will have telephone/video-conference visits via a telephone and/or a HIPAA compliant video conferencing platform, Webex with the research assistant and study clinician every two weeks. The RA will check Hamilton Rating Scale for Depression (HRSD) and Hamilton Anxiety Rating Scale (HARS) at each call. The study clinician will then evaluate the participant and complete the Clinical Global Impressions (CGI) Severity and Improvement. If the participant requests or significant clinical worsening in the

judgement of the study clinician occurs, then the participant will be brought to NYSPI for in person evaluation.

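### The starting-drug rule looks only at escitalopram history in the current episode, and the exclusions miss a reaction to one drug plus failure of the other, so a few eligible histories lead to an unsuitable starting drug

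*Protocol*

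**What the plan says.** Study Procedures, item 1, says that after consent "the participant will be begun on either escitalopram 10mg or duloxetine 30mg", and then that "The default medication will be escitalopram". The only stated reason to begin on the alternative is this: "Participants who have not responded to or not tolerated escitalopram in the current depressive episode will be started on duloxetine".

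Two exclusion criteria use medication history. The first is "History of allergic or adverse reaction to escitalopram and duloxetine", with no limit to the current episode. The second begins "Non-response to adequate trial of escitalopram (at least 4 weeks at dose of 20mg) and duloxetine", goes on to require four weeks of duloxetine at 60 mg, and applies to the current episode only. The population description joins the two drugs in the same way ("history of allergic or adverse reaction to escitalopram and duloxetine, (2) non-response to adequate trial of escitalopram"), so the conjunction is not a slip in one table.

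Study Procedures, item 2, deals with intolerance after treatment has begun. For a higher dose: "Subjects unable to tolerate the higher dose of study medication will have their dose reduced to the previously tolerated dose". For the first dose: "Subjects unable to tolerate the beginning dose of study medication will be tried (if possible given their history) on the other study medication". This is the only place where past history limits which study drug is given.

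**The concern.** The exclusions and the starting rule do not fit together, and this leaves two gaps.

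- **Earlier-episode escitalopram reaction.** Exclusion 1 removes a patient only for reactions to both drugs. Someone who reacted to escitalopram in a past episode and has no duloxetine problem is eligible. The starting rule does not look at past episodes, so this patient defaults to escitalopram.
- **Mixed history.** A reaction to one drug with a failed adequate trial of the other this episode meets neither exclusion. A patient who has not responded to escitalopram and once reacted to duloxetine is directed to start duloxetine.

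What is at stake is mainly avoidable re-exposure to a drug with a recorded reaction. Starting a drug that has already failed an adequate trial is a question of expected benefit, not of safety.

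**Working it through.** The plan gives no figure to reproduce. The check is to apply the written rules to every combination of histories.

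**Inputs.** Exclusions 1 and 2 are taken from Inclusion/Exclusion Criteria, and the starting rule from Study Procedures, item 1. Each drug has one of four histories: none; a reaction in an earlier episode; a reaction in the current episode (taken to mean not tolerated); adequate-trial non-response in the current episode. That gives 4 × 4 = 16 combinations. Each cell shows the drug started, and an asterisk marks a conflict.

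| Escitalopram history | Duloxetine: none | Duloxetine: earlier reaction | Duloxetine: current reaction | Duloxetine: adequate-trial non-response |
|---|---|---|---|---|
| None | escitalopram | escitalopram | escitalopram | escitalopram |
| Earlier reaction | escitalopram* | excluded | excluded | escitalopram* |
| Current reaction | duloxetine | excluded | excluded | duloxetine* |
| Adequate-trial non-response | duloxetine | duloxetine* | duloxetine* | excluded |

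**Results.**
- Excluded: 2 × 2 = 4 (reactions to both) + 1 (non-response to both) = 5. Eligible: 16 − 5 = 11.
- Conflicts: 5 of the 11. Four start a drug with a recorded reaction. One (current escitalopram reaction, duloxetine failure) starts a drug that failed an adequate trial.
- In one of the 5 (earlier escitalopram reaction, no duloxetine history) only the starting drug needs to change. The other 4 are the mixed cases, where neither drug suits.
- Combinations with no suitable drug: 5 already excluded + 4 mixed = 9. The exclusions therefore catch most of them.

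**A fifth history.** Adding current-episode non-response short of an adequate trial gives 5 × 5 = 25 combinations: 5 excluded, 20 eligible and 9 conflicts. Seven of the 9 start a drug with a recorded reaction, and 2 start a drug that failed an adequate trial.

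**Reading the conjunction as \"either drug\".** On the 16-cell grid only the cell with no history on either side would stay eligible, and the conflicts would vanish. But the duloxetine-start rule would then have almost no one to act on, and the history proviso in item 2 would have little purpose. The protocol evidently means to enrol patients for whom one drug is unsuitable.

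**Likely numbers.** Background, Significance and Rationale reports that only one third of the parent-study patients in question had any past medication treatment. If that held here (an assumption), 25 × 1/3 ≈ 8 enrolled patients would have had any. A conflict needs a problem with one or both of two particular drugs, so it would involve only a fraction of those 8.

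**The case against.** The best reply is that harm requires a prescriber to follow the text mechanically. Reaction history is taken by clinical interview. A physician or nurse practitioner discusses the risks of both drugs and the option of no treatment (Consent Procedures). Item 1 allows either drug and calls escitalopram only a default. Other medication and psychotherapy are listed as alternatives, and the study physician may withdraw a patient on clinical judgement. Side effects are assessed at each planned visit, and many recorded adverse reactions will be mild effects that do not rule out a retrial at the lowest dose.

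Much of this stands, and it keeps the expected impact small. It does not close the gap. None of these provisions sets a rule for the starting drug, and the dose-reduction and withdrawal provisions act after exposure. The history proviso governs only the later switch. In the mixed case the duloxetine instruction is directive, and choosing between two unsuitable drugs does not help. The clinician can advise against entry, but no criterion says so.

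A reader might infer from 5 of 11, or 9 of 20, that close to half of patients are exposed. The counts do not support that. They are unweighted profiles, in which a patient with no drug history counts the same as one with two rare problems, and they treat every recorded reaction as clinically significant. They are upper limits on the profiles in conflict and say nothing about frequency.

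**Conclusion.** The point holds as a minor defect in the treatment-assignment and eligibility wording. Followed literally, the starting rule begins escitalopram in an eligible patient with an earlier-episode reaction to it, and the exclusions admit the mixed case. On the 16-cell grid that is 5 of 11 eligible profiles: 4 concern re-exposure after a reaction and 1 concerns benefit. The count assumes that a current-episode reaction means not tolerated and that every reaction matters clinically.

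The documents do not give the number of patients affected. Given the low rate of past medication treatment it is likely to be small, and clinical judgement would probably prevent most cases.

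Two stronger conclusions are not supported. One is that the exclusions fail generally for patients with problems on both drugs: they already remove reactions to both and adequate-trial non-response to both. The other is that the trial's results are compromised: no endpoint, test or sample size depends on this rule.

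**What to change.** **Study Procedures, item 1.** Start duloxetine in patients with an allergic reaction to escitalopram, or intolerance of its starting dose, in any episode, and in those covered by the existing current-episode wording, which stays. Add an overriding sentence: no patient is started on a drug to which they have had an allergic reaction, or whose starting dose (escitalopram 10 mg, duloxetine 30 mg) they could not tolerate, in the study clinician's judgement. Tying the bar to the starting dose fits the dose-reduction rule in item 2, because a reaction seen only at a higher dose does not rule the drug out.

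**Description of subject population and Inclusion/Exclusion Criteria.** Also exclude patients for whom one drug is ruled out by such a reaction and the other by current-episode adequate-trial non-response.

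**Effect.** If every reaction in the grid is of this kind, the 16 combinations become 5 + 4 = 9 excluded, 4 starting escitalopram and 3 starting duloxetine, with no conflicts. On the 25-cell grid no patient is started on a drug with such a reaction.

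Some cases are best left to the clinician. A patient with escitalopram non-response short of an adequate trial and a duloxetine reaction is barred from duloxetine, but no rule should force a return to escitalopram. Nor should every current-episode intolerance count as a bar, since it may have arisen only at a higher dose. A start on duloxetine after it failed an adequate trial remains possible when escitalopram had only a short trial or was not tolerated only at the higher dose. That is a matter of benefit, not safety.

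**Cost.** A sentence or two in three places. No new data are needed, because the history already comes from the clinical interview and IRB 7489. Possibly zero or one fewer eligible patient, only among those who have already taken both drugs.

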6. Following the 8 weeks of open treatment, participants will be eligible for 3 months of post protocol open antidepressant treatment. They will continue to receive referrals for PTSD treatment as specified in IRB 7489.

You can upload charts or diagrams if any

Criteria for Early Discontinuation

Criteria for Early Discontinuation

If a patient discontinues medication due to tolerability problems, ineffectiveness, patient preference, or other reasons, the patient will be dropped out of the study and enter the 3 month long open treatment phase. Appropriate medication options will be discussed with the patient based on their symptoms and history. If the patient wishes, they will be provided referrals for psychotherapy or treatment options outside of our research clinic. No further research measures will be conducted once a patient enters the open treatment phase.

Patients in all treatment cells will be discontinued from the acute treatment phase if there is there is a rating of 6 (much worse) or 7 (very much worse) on the CGI—I for 2 consecutive weeks. Patients may also be discontinued from the study if this is indicated in the clinical judgement of the study physician and/or principal investigator. Patients receiving escitalopram/duloxetine may continue receiving the same medication if clinically indicated after being dropped from the study. No further research measures will be performed on patient dropped from the study.

Patients will be informed that should they experience a crisis or acute symptom worsening between scheduled weekly appointments, they should call their study clinician via the clinic office/research coordinator or the 24 hr doctor on call pager for CAAM. The study physician will evaluate the patient and make appropriate follow up arrangements, which may include activating EMS, calling the relevant mobile crisis team, or scheduling pt for immediate outpatient appointment in the CAAM. Patients in crisis will be assessed immediately and appropriate clinical action taken as above (i.e., those meeting criteria for early discontinuation will be dropped from the study and treated openly).

Blood and other Biological Samples

Please create or insert a table describing the proposed collection of blood or other biological specimens. No additional blood will be drawn over and above what was already drawn for IRB 7489.

Assessment Instruments

Create a table or give a brief description of the instruments that will be used for assessment

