Antidepressant Response in Older Adults
with Comorbid PTSD and MDD

Protocol ID 8111
NCT04697693

Statistical Analysis Plan

Document Version Date: January 29th, 2021

Statistical Analysis

Descriptive statistics for the sample at baseline will be computed and reported in terms of means with standard deviations. The hypotheses under investigation are that (1) individuals with comorbid PTSD and MDD will experience significant depressive symptom improvement with antidepressant treatment and that (2) cognitive and physical functioning will likewise significantly improve following antidepressant treatment. To investigate these hypotheses, paired samples t-tests will be used to analyze the within-subject change from pre- to post-treatment on depressive symptom severity (Hamilton Rating Scale for Depression [HRSD]), cognitive functioning (NIH Toolbox total score), and physical functioning (gait speed).

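### The SAP defines neither the HRSD analysis set nor the post-treatment score and leaves the biweekly HRSD ratings unused; a repeated-measures model is a cheap improvement

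*Protocol*

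**What the plan says.** **Who leaves, and what is then measured.** The protocol's section on Criteria for Early Discontinuation gives the main rule: "If a patient discontinues medication due to tolerability problems, ineffectiveness, patient preference, or other reasons, the patient will be dropped out of the study". Sustained CGI-I ratings of 6 or 7 also lead to discontinuation. The section says twice that measurement then ends: "No further research measures will be conducted once a patient enters the open treatment phase", and again "No further research measures will be performed on patient dropped from the study". Study Procedures, item 2, adds one more way out: "Participants unable to tolerate the beginning dose of either study medication will be dropped from the study and enter post protocol open treatment".

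**What is measured before that.** Study Procedures, item 3, has HRSD rated at each two-weekly contact, ahead of the clinician's rating: "The RA will check Hamilton Rating Scale for Depression (HRSD) and Hamilton Anxiety Rating Scale (HARS) at each call", followed by "The study clinician will then evaluate the participant and complete the Clinical Global Impressions (CGI) Severity and Improvement". Item 4 treats Week 8 as the endpoint, and it is the only point after baseline at which cognition and physical function are tested.

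**What is planned.** Description of Subject Population asks for 20 completers from 25 enrolled. Hyp 1 also predicts a response rate above 50%, without defining response or its denominator. The SAP is a single paragraph: "paired samples t-tests will be used to analyze the within-subject change from pre- to post-treatment on depressive symptom severity", with the same test for NIH Toolbox total score and gait speed. It gives no analysis set, no rule for missing scores, no definition of the post-treatment score, and no use for Weeks 2, 4 and 6.

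**The concern.** A paired t-test uses only people who have both scores. If the second score is the Week 8 score, everyone dropped for ineffectiveness or worsening is left out of the HRSD result, although most of them would have on-treatment HRSD ratings already on file.

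Aim 1 is about effectiveness and there is no control group, so the size of the HRSD change is the main result. Leaving out people who did badly would make that change look larger and its confidence interval too optimistic. Because the post-treatment score is not defined, the analyst could also choose between a Week 8 and a last-available-score analysis after seeing the data, and the two err in opposite directions.

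**Working it through.** **1. Attrition implied by the plan.** 20 / (1 − 0.20) = 25, so the two enrolment figures agree at (25 − 20) / 25 = 20% attrition. The 20% is back-calculated. The documents give no alpha, power, SD or change score, so every outcome input below is assumed.

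**2. Simple algebra.** Let *d* be the share dropping out and *r* the dropouts' mean improvement divided by the completers'. The completer mean exceeds the all-enrolled mean by 1 / ((1 − d) + d·r) − 1. At d = 0.20:
- r = 1: 0%
- r = 0.67: 1 / 0.934 − 1 = 7.1%
- r = 0.5: 1 / 0.9 − 1 = 11.1%
- r = 0.27: 1 / 0.854 − 1 = 17.1%
- r = 0: 25%

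**3. Simulation.** Assumed: n = 25; HRSD means 24, 21.5, 19.5, 17.5, 16 at Weeks 0, 2, 4, 6, 8 (true change −8.0 had all stayed on treatment); SDs 4, 6, 7, 7.5, 8; AR(1) correlation 0.75. The change SD is √(4² + 8² − 2·4·8·0.75⁴) = 7.73, so the standard error with 20 completers is 7.73 / √20 = 1.73. Dropout is 4% at random before Week 2, then logistic with slope 0, 1 or 2 per SD of change from baseline, set to lose about 4.8 of 25. On average 3.8 of those 4.8 have at least one post-baseline HRSD. There were 6,000 trials per setting (1,200 for coverage).

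| Dropout depends on | Completer mean | Excess over 8.0 | Unstructured model mean | 95% CI coverage, completers / model |
|---|---|---|---|---|
| nothing | −8.01 | 0% | −8.00 | 95.8% / 96.8% |
| observed score, slope 1 | −8.57 | 0.57 (7%) | −7.99 | 93.7% / 95.2% |
| observed score, slope 2 | −8.91 | 0.91 (11%) | −7.98 | 91.6% / 95.6% |
| unseen next score, slope 1 | −8.87 | 0.87 (11%) | −8.49 | 91.1% / 93.7% |
| unseen next score, slope 2 | −9.38 | 1.38 (17%) | −8.85 | 87.4% / 91.1% |

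Cross-check on the second row, where dropouts would have changed by −5.6: 0.808 × 8.57 + 0.192 × 5.6 = 8.00. In the last two rows the model removes (8.87 − 8.49) / 0.87 = 44% and (9.38 − 8.85) / 1.38 = 38% of the bias. The completer t-test is significant in 99.3% to 100% of trials. With outcome-related dropout, the excess is 4–10% at 3 dropouts and 11–26% at 7.

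**4. The other reading.** If post-treatment means last available score, with those lost before Week 2 counted as no change, the same model gives −6.7 to −7.6. That understates the Week 8 change by 0.4 to 1.3 points (5–16%).

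**5. Covariance structure.** In a further run with the same inputs, completers gave −8.55 and −8.90 under observed-score dropout, and a compound-symmetry model gave −8.26 and −8.42. It leaves 0.26 of 0.55 and 0.42 of 0.90, about half the bias, although missingness depends only on observed scores. Heterogeneous AR(1) removed all of it, but the data were generated with that structure. Heterogeneous Toeplitz was not run; it contains heterogeneous AR(1) as a special case.

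**6. Response rate.** 11 of 20 completers is 55%; 11 of 25 is 44%. With 20 completers, the two denominators fall on opposite sides of 50% only at 11 or 12 responders, 2 of 21 possible counts.

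**The case against.** The strongest reply is that the documents never say HRSD will be a completer analysis. The 20 completers are an enrolment figure, and the post-treatment score could be the last one available. This stands: the upward direction depends on the completer reading, and what is firmly established is the ambiguity.

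A reader might infer that the plan inflates the HRSD result by 7–17%. The documents do not support that. No change score, SD or dropout mechanism is given, and dropout unrelated to outcome gives no bias. Since HRSD is rated before the CGI at each contact, CGI-driven exits follow an observed score, which corresponds to the 7–11% rows. Anything above that needs dropout driven by a score nobody saw. People who leave for tolerability or preference may have improved.

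It can also be said that little hangs on it: the excess is below one standard error, significance is safe, and an open single-arm study of about 25 people cannot attribute the change to drug anyway. All true, and it limits the weight of the point. It does not justify setting aside scores already scheduled when the size of change is the main result.

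Four objections to the remedy also stand:
- An unspecified simpler covariance structure could lose half the benefit.
- Change had everyone stayed on treatment is a strained target for people who tolerate neither starting dose.
- Weeks 2 to 6 are remote by default, while Weeks 0 and 8 are in person.
- No section explicitly lists an HRSD at Week 0. The Lay Summary mentions only baseline testing, and the eligibility HRSD comes from IRB 7489.

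**Conclusion.** The point holds as a cheap improvement. The SAP leaves the HRSD analysis set and post-treatment score open and does not use ratings that most dropouts would have. On the natural reading, Week 8 completers, improvement is overstated if dropout is related to poor outcome, which two of the listed exit routes (ineffectiveness and worsening) make plausible. On assumed inputs at about the plan's own attrition, the excess runs from zero to about 1.4 points on a true change of 8.0. Coverage of the nominal 95% interval falls to about 87–94% when dropout is outcome-related.

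Two further inferences go too far. First, nothing here threatens the finding of a significant HRSD change. Second, the absence of dropouts from the cognition and gait tests does not show that those results are inflated: the discontinuation reasons concern depression outcome and tolerability, and the documents give nothing that fixes the direction for the other two measures.

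**What to change.** Amend the SAP as follows.

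1. Define the HRSD analysis set as all participants who take at least one dose, post-treatment as Week 8, and baseline as the Week 0 HRSD. Confirm that HRSD is rated at Week 0 and not carried over from IRB 7489.
2. Make the primary HRSD analysis a mixed model for repeated measures on Weeks 0, 2, 4, 6 and 8, reporting Week 8 change with a 95% CI. Use an unstructured covariance and name heterogeneous AR(1) or Toeplitz now as the fallback; rule out compound symmetry. State that the model estimates change had participants stayed on treatment, removes only part of the bias if dropout depends on unseen scores, and combines remote with in-person ratings. Keep the completer paired t-test as a sensitivity analysis.
3. If the Hyp 1 response rate is reported, define response and give the rate over all treated participants with early discontinuation counted as non-response, and the completer rate alongside. Say that this is a conservative rule and answers a different question from the model.
4. Label cognition and gait as completer analyses, and report the number, reasons and baseline values of those missing.

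The cost is SAP wording and one standard model, with no new visits if the Week 0 rating is confirmed. In the simulation the model's intervals were slightly wider (mean width 6.8 to 7.4 points against 6.5 to 7.1). Its root-mean-square error was about equal when dropout was unrelated to outcome (1.69 against 1.70) and lower otherwise (1.70 to 1.79 against 1.77 to 2.08). The estimate is likely to look less favourable than the completer mean. No dose, stopping or treatment rule changes.
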